## 7.2 Study sites

#### 7.2.1 Study Sites for Aims 1 and 2

Aims 1 and 2: Coordinating Center will collect health system data from Duke University Health System and Vanderbilt University Medical Center, and Medical University of South Carolina, and Wake Forest University Health Sciences via the STAR CRN using CDM.

#### 7.2.2 Study Sites for Aim 3

Aim 3: Duke University Health System, Vanderbilt University Medical Center, Medical University of South Carolina will identify patients and health care providers for interviews; Case Western Reserve University will identify only health care providers for interviews.

Participants will be identified/consented for the qualitative interviews from the following sites:

Duke University Health System (DUHS): Patients & Health Care Providers
 Vanderbilt University Medical Center (VUMC): Patients & Health Care Providers
 Medical University of South Carolina (MUSC): Patients & Health Care Providers

Case Western Reserve University (CWRU): Health Care Providers

## 7.3 Inclusion and exclusion for Aims 1, 2 and 3

#### 7.3.1 Patient EHR data for Inclusion criteria for Aims 1 and 2

- (1) Race equals Black/African-American, American Indian/Alaska Native, Asian, Native Hawaiian/Pacific Islander, or More than one race, and/or Ethnicity equals Hispanic or Latino;
- (2) Documented evidence of HIV positive status (HIV positive diagnosis (ICD10 codes B20-B24, or ICD9 codes 042, V08) and prescription of antiretroviral therapy (ART));
- (3) Documented evidence of elevated AtheroSclerotic CardioVascular Disease risk (ACC/AHA ASCVD 10 year risk ≥5%²⁴, or Framingham Cardiovascular Disease 10 year risk ≥5%²⁵) after HIV diagnosis. The date when the patient first meets either of these CVD risk thresholds and with 1 prior encounter not having CVD risk score defines the **index** time-point for Aim 1 of this study. These risk calculations depend on sex, age, body mass index, diabetes, current smoking, total cholesterol, HDL cholesterol, systolic blood pressure, and treatment for hypertension (defined from diagnosis codes). If cholesterol measures are not available, then body mass index may be used in place of lipids in the Framingham risk calculation; **NOTE: must have at least one prior encounter within 365 days within health system prior to index**
- (4) Presence of a modifiable risk factor: hypertension, diabetes, elevated total cholesterol, elevated LDL cholesterol and/or tobacco use.

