Then, DCRI will take the query data that the sites provide to identify and further stratify data for potential cohort of patients, based on additional clinical characteristics. At the earliest clinical contact within look back period, we will identify HIV status according to ICD9/10 codes and prescription of ART. We will include individuals >18 years of age and < 99 years of age, plus will ascertain time-updated data for the following potential characteristics:

hemoglobin, creatinine (or glomerular filtration rate), age, sex, race, ethnicity, insurance status, total cholesterol, HDL cholesterol, LDL cholesterol, systolic blood pressure, prescription of anti-hypertensive medications, family history of coronary artery disease, presence of diabetes, previous diagnosis of any acute myocardial infarction, hospitalization for heart failure, acute coronary syndromes, stable or unstable angina, arterial revascularization, stroke, transient ischemic attack and peripheral arterial disease presumed to be of atherosclerotic origin determined by ICD9/10 codes. Behavioral factors are smoking status, number of clinic visits per year, length of time between clinic visits and missed appointments with specialist after referral. Data will also be ascertained on HIV viral load, CD4 count, prescription of any ART and length of time on all medications. This list captures the majority of the data related to our scientific aims and will be modified as the availability of these data are discovered.

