## 12 Data analysis & statistical considerations

#### 12.1 Analysis Plan for Aim 1

For this aim, the primary outcome variable is referral to a cardiology specialist within 6 months of baseline. This will be measured as a binary variable, with 'yes' defined if there is documented evidence that a referral is made within 6 months of becoming eligible by CVD risk score and kept within 3 months of referral, and 'no' otherwise. We will also determine the time from baseline to cardiology referral and the time until the first visit with the cardiology specialist.

We will consider a number of patient and provider factors evaluated at baseline that are potentially associated with referral to a cardiology specialist. Patient factors will include demographic factors (age, sex, race, ethnicity), level of ASCVD risk, Charlson comorbidity index, SES (e.g.; 5 digit zip code, health insurance ([yes/no]), type of health insurance (Medicare, Medicaid, private, Ryan White, etc.), and history of keeping appointments during 2 years prior to baseline. Provider factors will include primary management strategy (coprimary management defined as having both an HIV doctor and Primary Care Practitioner vs. HIV provider as primary care), and years of practice since training. Cardiologist availability will be a site-determined variable. Based on prior literature, we are specifically considering sex as a biological variable that may be related to specialty referral. 

Baseline characteristics of the cohort will be summarized overall and by referral status. We will include the patient and provider factors described above, as well as vital signs (including weight, body mass index and blood pressure), laboratory measures (particularly total and HDL cholesterol, CD4 cell count, HIV viral load), and relevant medications (ART and cardiovascular medications). We will document the patterns of HIV related CVD comorbidity in the study population, as the funding opportunity announcement specified.

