Starting with the population selected for Aim 1, we will create a sub-population by matching patients referred to a cardiology specialist (the primary outcome variable for Aim 1) to similar non-referred patients. The goal of this matching is to balance factors that may be confounders of the relationship between referral and cardiovascular outcomes. We will identify factors found to be associated with cardiology referral from Aim 1, as well as factors that are expected to be associated with outcomes such as, age, race, insurance status/type, ASCVD risk score, and comorbidity index. We will not seek to match on factors that may be associated with referral but unlikely to be directly associated with outcomes. For example, we may not want to match on cardiologist availability by site if this is only related to referral and not independently to outcomes. Variables that potentially modify the effect of referral (e.g., sex, race/ethnicity, insurance status) will be included among the matching factors. Patients will be matched within sites and year of baseline encounter.

For each patient referred to a cardiologist we will identify one non-referred patient (1:1 matching) within each site. We will match using values of the individual confounders, with an exact match on sex, race/ethnicity, insurance status/type, and to within a small caliper for continuous variables (e.g., ±5 years for age). Matched pairs will be identified using optimal matching. If this approach fails to identify an adequate number of matched pairs, then 1:1 matching will be implemented using a propensity score.

Once the matching has been implemented, the same baseline characteristics reported for Aim 1 will be summarized in the matched cohort by referral status. Metrics (e.g., standardized differences) will be reported to evaluate how well-balanced the referred and non-referred groups.

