For this aim, the primary outcome variable will be blood pressure control based on prevailing guidelines during the study period (blood pressure <140/90 mmHg). The co-primary outcome is lipid control, defined by prevailing guidelines during the study period. These outcomes will be evaluated longitudinally during 5-years of follow-up. Secondary outcome variables include time to the first major adverse cardiovascular event (MACE = cardiovascular death, myocardial infarction (MI)), stroke, heart failure hospitalization, peripheral artery disease procedure, coronary artery disease (based on diagnosis codes or coronary artery revascularization procedure), and all-cause death. Events ascertained from relevant diagnosis and procedure codes, and from a query of the National Death Index Plus, State Death records, Social Security Death Masterfile, Hospital death record and/or similar death record for causes of death including cardiovascular

death. We will also evaluate time to BP control and time to lipid control among patients who were not controlled at study start. For this Aim, "time zero" for the matched patient pair will be defined as the time from baseline (see Aim 1) when the referred patient kept their cardiology appointment. Events will be ascertained starting from time zero and until the end of follow-up. For each patient, end of follow-up will be defined as the date of the last outcome event or health system encounter without an event, occurring ≥3 months prior to the retrospective study review period of December 31, 2020 of the EHR.

To evaluate the association between cardiology referral and subsequent blood pressure and lipid control (coprimary outcomes), we will first evaluate these measures between referred and non-referred patients at baseline, and then compare prevalence and time trends between referred and non-referred patients using methods appropriate for longitudinal data analysis. For example, we will explore whether the proportion of patients with adequately controlled BP at each year is higher in referred compared to non-referred patients. Because these analyses are conducted in the matched population, the results are adjusted for the potential confounders included in the identification of the matched pairs.

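### The co-primary yearly BP and lipid control comparison in Aim 2 relies on matching alone for adjustment, and baseline BP, lipids and treatment are named neither as matching factors nor as model terms

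*Combined protocol and SAP*

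**What the plan says.** All references are to the combined protocol and SAP.

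- **Adjustment (Section 12.2).** The co-primary outcomes are BP control (below 140/90 mmHg) and lipid control, followed for 5 years. Both are first looked at by group at baseline. Prevalence and time trends are then compared with longitudinal methods that are not named; the example given is the proportion controlled at each year. On confounding, the section says: "Because these analyses are conducted in the matched population, the results are adjusted for the potential confounders included in the identification of the matched pairs".
- **Matching (Section 12.2).** Outcome-related factors are introduced as "such as, age, race, insurance status/type, ASCVD risk score, and comorbidity index". Factors that Aim 1 finds to be associated with referral are added. Sex, race/ethnicity and insurance are matched exactly, within site and baseline year, and age is the only caliper example.
- **Aim 1 factors (Section 12.1).** BP, cholesterol and cardiovascular medications are not among the candidate patient and provider factors. They are added to the descriptive summary: "We will include the patient and provider factors described above, as well as vital signs (including weight, body mass index and blood pressure", followed by laboratory measures and medications.
- **Risk score (Section 7.3.1).** The listed inputs are "sex, age, body mass index, diabetes, current smoking, total cholesterol, HDL cholesterol, systolic blood pressure, and treatment for hypertension". In addition: "If cholesterol measures are not available, then body mass index may be used in place of lipids in the Framingham risk calculation".
- **Balance (Section 12.2).** After matching, "the same baseline characteristics reported for Aim 1 will be summarized in the matched cohort by referral status", with metrics such as standardized differences. No threshold or consequence is given.
- **Other use of baseline status (Section 12.2).** Time to control is also analysed among patients who start uncontrolled.

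**The concern.** Aim 2 is a non-randomised comparison. The baseline value of the outcome is an obvious candidate confounder and is usually a strong predictor of the follow-up value. If adjustment extends only to the matching variables, and the baseline outcome is not named among them, any imbalance left after matching passes into the yearly control rates. The plan would report that imbalance without correcting for it.

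The risk score does not close the gap. Two patients with the same score can have different BP and lipids. Diastolic BP, LDL cholesterol and lipid-lowering treatment are not among its listed inputs, although BP control depends on diastolic pressure. Where body mass index replaces cholesterol, the Framingham score carries no lipid information.

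Precision is also at stake, mainly for BP control, where the planned power is only above 70%.

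**Working it through.** **Inputs from Section 12.2.1:** 300 per group; control rates of 30% (BP) and 45% (lipids) in the non-referred group; increases of 10 and 15 points. A two-sided 0.05 level is stated beside the Cox analysis and is assumed here for the co-primary outcomes.

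**Inputs not in the documents (assumed):** a baseline difference d of 5 to 10 points in the proportion controlled, and a within-patient correlation φ of 0.3 to 0.6 between baseline and follow-up control.

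**1. The plan's own power.** Power = Φ[(Δ − 1.96·SE0)/SE1], where SE0 = √(2p̄(1−p̄)/n) and SE1 = √((p1(1−p1)+p2(1−p2))/n).
- BP, 30% v 40%: SE0 = √(2×0.35×0.65/300) = 0.03894 and SE1 = √((0.21+0.24)/300) = 0.03873. Power = Φ(0.611) = 72.9%; the plan states above 70%.
- Lipids, 45% v 60%: SE0 = 0.04077 and SE1 = 0.04031. Power = Φ(1.739) = 95.9%; the plan states above 95%.

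Both figures reproduce when the increases are read as absolute points.

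**2. Carry-over of a baseline difference.** Shift in the unadjusted follow-up difference = φ·d.
- d = 5 points: 0.3×5 = 1.5 to 0.6×5 = 3.0 points.
- d = 10 points: 0.3×10 = 3.0 to 0.6×10 = 6.0 points.

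The standardized difference, d divided by the root of the mean of the two binomial variances, is 0.107 (5 points) and 0.211 (10 points) at 30%, and 0.100 and 0.201 at 45%.

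**3. Consequence for the unadjusted test at 300 per group.** The rejection rate with no true effect is Φ[(−1.96·SE0 − b)/SE1] + 1 − Φ[(1.96·SE0 − b)/SE1], with b = φ·d. The power columns apply if referred patients start less controlled; the true effects are 10 points (BP) and 15 points (lipids).

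| Shift b | BP, no effect | Lipids, no effect | BP power | Lipid power |
|---|---|---|---|---|
| 0 | 5% | 5% | 72.9% | 95.9% |
| 1.5 points | 6.8% | 6.6% | 59.3% | 91.3% |
| 3 points | 12.4% | 11.4% | 44.3% | 83.8% |
| 6 points | 34.6% | 31.2% | 18.1% | 59.7% |

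A simulation (6,000 runs) gave 6.4% to 33.6% (BP) and 6.8% to 32.9% (lipids) without adjustment, and 4.7% to 5.3% with baseline control status as a covariate. The second result is largely built in, because the simulated imbalance lay only in the variable being adjusted for.

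**4. Precision if the groups are balanced.** A baseline term multiplies the residual variance by 1 − φ², that is 0.91 (φ = 0.3) to 0.64 (φ = 0.6). The effective n is 300/0.91 = 330 to 300/0.64 = 469 per group. BP power becomes 76.9% to 89.6%, and lipid power 97.2% to 99.6%. This is a linear approximation at a single time point, not a calculation for repeated binary outcomes.

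**5. Timing.** Section 12.1 counts a referral if "a referral is made within 6 months of becoming eligible by CVD risk score and kept within 3 months of referral". The visit that defines time zero can therefore fall up to 6 + 3 = 9 months after index, so which measurement counts as baseline matters.

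**The case against.** The strongest reply is that the plan's own rule already reaches these variables. Matching is meant to balance confounders, the list is open, and when the outcome is BP or lipid control the baseline BP and lipids clearly qualify. The named ASCVD score contains systolic BP, total and HDL cholesterol and treated hypertension. Baseline values are compared by group, balance is reported, trends are compared, and the time-to-control analysis conditions on starting status. A trend contrast and a baseline covariate are both legitimate and answer somewhat different questions. The missing term is also one part of a wider gap, since no longitudinal model is named at all, and it should not be counted twice if that gap is raised separately.

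Much of this stands. It rules out the claim that the plan excludes or ignores baseline values. It does not supply the missing commitment. Nothing says that the baseline outcome will be matched on or modelled, or what follows if imbalance is seen. The sensitivity analyses carried over from Aim 1 name no baseline adjustment. The time-to-control analysis is additional and covers a subset. A trend contrast could account for starting level, but the plan does not say that the baseline measurement is in the series or that the trend is the co-primary test, and Section 12.2.1 powers a difference in control rate.

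It is also fair to say that the upper end of the illustration needs a 10-point imbalance left after matching on the risk score, together with φ = 0.6. No figure in the documents supports that combination, and the planned balance metrics would show a standardized difference of about 0.2.

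**Conclusion.** The point holds as a gap in pre-specified confounding control for both co-primary outcomes, and it should be fixed. Matching is the only adjustment stated, and no baseline BP, lipid or treatment variable is named in it or in a model. That omission is certain from the text.

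A reader might infer that the Aim 2 results will be biased, or biased in a particular direction. The documents do not support this: they give neither the imbalance after matching nor the baseline to follow-up correlation, and the risk score gives partial control. The shift of 1.5 to 6 points, the rejection rates of about 7% to 35% (BP) and 7% to 31% (lipids), and the power gains all rest on assumed values. A reader might also infer that the sample-size statement is wrong; it is not.

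**What to change.** In Section 12.2, state that the longitudinal co-primary models include:
- baseline systolic and diastolic BP in the BP control model;
- baseline lipid values in the lipid control model;
- baseline antihypertensive and lipid-lowering treatment.

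Take all of these at or before the Aim 1 index date, for both members of each pair. A looser cut-off, such as any time before the cardiology visit, would admit treatment started around or after the referral decision. Hypothesis 2a in Section 4 treats medication management and statin use as mediators, so adjusting for such treatment could remove part of the association under study.

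Alternatively, if the time-trend contrast is meant to be the co-primary test, say so and include the baseline measurement in the modelled series.

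State how patients without baseline cholesterol are handled in the lipid model. Adding the baseline variables to the caliper or propensity-score match is optional, because it may lose pairs.

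The cost is a few model terms, some SAP wording and the missing-lipid rule. Most of the data are already planned: Section 8.1 lists "total cholesterol, HDL cholesterol, LDL cholesterol, systolic blood pressure, prescription of anti-hypertensive medications" for extraction, and Section 12.1 already summarises BP and cardiovascular medications at baseline.

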To evaluate the association between cardiology referral and CVD events (secondary outcomes), the cumulative incidence of primary and secondary outcomes will be summarized in the referred and matched non-referred patients. Follow-up will be censored at the earliest of 8 years or end of follow-up. For each outcome variable a Cox regression model will be fit, and the hazard ratio (referral vs. not referred) and 95% CI, and p-value will be reported. The Cox regression analysis will account for the matched pairs design using the empirical sandwich variance estimate. Statistical significance will be determined at the two-sided 0.05 level.

The relationship between referral status and outcomes will also be evaluated within subgroups of primary interest: sex, race, ethnicity and insurance as defined in Aim 1. Evidence for a differential association between referral status and CVD outcomes for different subgroups will be quantified using an interaction test in the Cox regression analysis. The considerations and approaches outlined in Aim 1 regarding missing data and sensitivity analyses will also be applicable for Aim 2.

#### 12.2.1 Expected power and sample size for Aim 2

Aim 2 expected power and sample size: With an anticipated cardiology referral rate of 20-25% among 1,200-1,500 patients included in Aim 1, the sample size in the matched cohort study is expected to be 250-375 per group. These patients will be accrued into the study over 5 years (2012-2016) and then followed to evaluate BP and lipid control, and for cardiovascular events for up to 8 years through December 31, 2020. For the primary endpoints, the rates in the non-referred group are anticipated to be 30% and 45% for BP and lipid control, respectively. With 300 per group, the study is predicted to have >70% power to detect a 10% increase in rate of BP control, and >95% power to detect a 15% increase in rate of lipid control due to cardiology referral. For the secondary endpoints, the rate of MACE events is anticipated to be fairly low (i.e., a cumulative incidence ~5% at 5 years and ~10% at 10 years) and we anticipate modest power to detect even large reductions in risk of CVD events due to cardiology referral. However, this aim will provide useful information about clinical event rates and estimates of the potential to effect event rates that could be attributed to cardiology referral.

#### 12. 3 Analysis Plan for Aim 3

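### The co-primary BP comparison includes patients without hypertension, and the 30% control rate behind the >70% power is not shown to fit that mixed cohort

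*Combined protocol and SAP*

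**What the plan says.** Section 7.3.1, inclusion criterion 4, is met by any one of "hypertension, diabetes, elevated total cholesterol, elevated LDL cholesterol and/or tobacco use". Section 12.2 builds the Aim 2 cohort from the Aim 1 population: "For each patient referred to a cardiologist we will identify one non-referred patient (1:1 matching) within each site".

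The named matching factors in Section 12.2 are age, sex, race/ethnicity, insurance, ASCVD risk score, comorbidity index, site and year of baseline, plus whatever Aim 1 finds to be associated with referral. Hypertension status and baseline BP are not named. They enter only through the risk score, which Section 7.3.1 says depends on systolic BP and hypertension treatment among other items.

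Section 12.2 also says that "the primary outcome variable will be blood pressure control based on prevailing guidelines during the study period", with <140/90 mmHg as the threshold, and compares prevalence and time trends in the matched population. Only the additional time-to-control analysis is limited, to patients not controlled at the start.

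Section 12.2.1 says "the sample size in the matched cohort study is expected to be 250-375 per group" and "the rates in the non-referred group are anticipated to be 30% and 45% for BP and lipid control, respectively", and concludes: "With 300 per group, the study is predicted to have >70% power to detect a 10% increase in rate of BP control". It gives no source for the 30% and no expected share of patients with hypertension.

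**The concern.** A smoker or a patient with diabetes whose BP is normal can be eligible, is below 140/90 at baseline, and counts as controlled. Such patients have little room to improve on the co-primary outcome. If they make up a material share of the cohort, two things follow.

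- Any effect in patients with hypertension is averaged with a smaller effect, or none, in the rest. The power for 30% against 40% then may not describe the comparison that will be made.
- Baseline BP is a strong candidate confounder of later BP control, and the matching balances it only indirectly. Two patients can have the same risk score with different BP, because age, smoking, diabetes and lipids also enter the score.

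**Working it through.** **Inputs from the documents.** Control of 30% against 40%, 300 per group, 1:1 (Sections 12.2 and 12.2.1). For alpha, the Aim 2 Cox paragraph says "Statistical significance will be determined at the two-sided 0.05 level"; no split between the co-primary outcomes is described.

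**Formula.** Two-proportion normal approximation with pooled variance under the null, where p̄ = (p1 + p2)/2:

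power = Φ{ [(p2 − p1) − 1.96·√(2p̄(1 − p̄)/n)] / √[(p1(1 − p1) + p2(1 − p2))/n] }

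**Step 1: the plan's own figure.** p̄ = 0.35. The null standard error is √(2 × 0.35 × 0.65/300) = 0.0389, and the alternative standard error is √((0.21 + 0.24)/300) = 0.0387. Power = Φ[(0.10 − 1.96 × 0.0389)/0.0387] = 72.9%, which agrees with >70%. Over the plan's own range it is 65.0% at 250 per group and 82.0% at 375. Reading the 10% as relative (30% to 33%) gives 12.1%, so absolute points are meant.

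**Step 2: does 30% fit a mixed cohort?** Let h be the hypertensive share, q the control rate in hypertensive patients and c the control rate in the rest. The documents give none of these. Overall control is hq + (1 − h)c. Setting this to 0.30 gives h = (c − 0.30)/(c − q).

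- q = 0, c = 0.85: h = 0.55/0.85 = 65%.
- q = 0, c = 1.00: h = 0.70/1.00 = 70%.
- q = 0.20, c = 0.90: h = 0.60/0.70 = 86%.

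So 30% overall needs a largely hypertensive cohort with very poor control.

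**Step 3: if 30% to 40% holds only in hypertensive patients.** Assume no effect in the rest. Then p1 = 0.30h + c(1 − h) and p2 = 0.40h + c(1 − h), so the difference is 0.10h. Example with h = 0.80 and c = 0.90: p1 = 0.24 + 0.18 = 0.42, p2 = 0.32 + 0.18 = 0.50, power 50%. The last column keeps 30% against 40% with 300h per group.

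| Hypertensive share h | Difference, all patients | Power, all patients (c = 0.90) | Hypertensive per group | Power, hypertensive only |
|---|---|---|---|---|
| 90% | 9 points | 61% | 270 | 68% |
| 80% | 8 points | 50% | 240 | 63% |
| 70% | 7 points | 40% | 210 | 58% |
| 50% | 5 points | 24% | 150 | 44% |

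Varying c from 0.85 to 1.00 moves the all-patient figures by no more than about two points. All-patient power falls below 70% once h is under about 97.5%. The restricted analysis needs 281 per group for 70%.

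**Step 4: if 30% to 40% holds in the whole cohort.** With h = 0.80, c = 0.90 and no effect in the rest, control in hypertensive patients would have to go from (0.30 − 0.18)/0.80 = 15% to (0.40 − 0.18)/0.80 = 27.5%, a gain of 12.5 points. The plan does not discuss this.

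**Step 5: if a 10-point gain holds in the whole cohort at a higher control rate.** Power at 300 per group is 69% for 50% to 60%, 73% for 60% to 70%, 81% for 70% to 80% and 93% for 80% to 90%. A higher control rate alone does not cost power; a smaller absolute difference does.

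All of this uses a single-time, unpaired test. The plan is longitudinal in matched pairs, and the documents give no correlation with which to refine the figures.

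**The case against.** The plan attributes the 30% to the non-referred group of the matched cohort, which is the group analysed, and the power reproduces for those inputs. A reader might infer from Step 3 that the >70% is wrong and true power is 24-50%. The documents do not support that: they give no hypertensive share, no control rate in the rest and no subgroup effect. Shares near 50% are unsupported, since the risk score used for entry includes BP and hypertension treatment and so favours hypertension.

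Two other inferences also fail. One is that referral cannot help a patient with normal BP. Control is followed for 5 years, and referral might prevent later loss of control, so zero effect in that group is an assumption. The other is that limiting time-to-control to uncontrolled patients shows the authors recognised a mixed cohort. Time to control can be defined only in such patients, so the limit would be there even if all had hypertension.

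It is also fair that Aim 2 concerns people at elevated CVD risk, not hypertension as such. The list of outcome-related matching factors is illustrative, so BP could still be added. Balance will be reported for the Aim 1 baseline characteristics, which include BP, but the plan does not say what follows if BP is unbalanced.

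A poorly built restriction would add problems. Time zero is the kept cardiology visit, up to 6 + 3 = 9 months after baseline by the Section 12.1 definition. A referred patient has a visit that day at which hypertension can be recorded; the matched patient need not. And if status is not matched and is independent within pairs, an 80% share leaves 300 × 0.8² = 192 pairs with both members hypertensive, and power of 54% against 50% for all patients.

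What stands after this is the unrestricted population, the unnamed baseline factors and the unexplained 30%.

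**Conclusion.** The concern holds in a conditional form. The documents establish that patients without hypertension can be in the co-primary BP comparison, that hypertension status and baseline BP are not named matching factors, and that the 30% has no stated source. A 30% control rate is hard to reconcile with a cohort holding a material share of patients with normal BP, so the >70% is not shown to apply to the population analysed. It is not shown to be false either.

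The size depends on two assumptions that the documents cannot settle: that the 10-point gain is confined to hypertensive patients, and the share they make up. Under the first, the all-patient analysis loses about 12 points of power at a 90% share and 23 at an 80% share (72.9% to 61% and 50%), and restriction recovers part of that without reaching 70%.

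A reader might extend the argument to lipid control. The documents do not support this: the outcome is defined through cited guidelines, and nothing shows a similar dilution.

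**What to change.** 1. Add hypertension status and baseline BP to the matching factors, both measured at or before the Aim 1 index date and not at the cardiology visit. Adjust the longitudinal BP model for baseline BP.
2. Make the co-primary BP comparison in pairs matched on having hypertension at index. Keep the all-patient comparison as a sensitivity analysis.
3. In Section 12.2.1, state which population the 30% describes, its source and the expected hypertensive share. Restate power for the expected number of hypertensive pairs, using the last column of the table if status is matched.
4. For lipid control, adjust for the baseline lipid value and state the population behind the 45%. No change of analysis population is called for.

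The cost is mainly SAP wording, because Sections 7.3.1 and 8.1 already rely on BP, diagnosis codes and antihypertensive prescriptions. The downsides are a smaller denominator for the BP outcome, possible loss of pairs from the extra matching factors, and a less favourable power figure.
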